For each of the symptoms scales/items in the EORTC QLQ-C30 and QLQ-LC13, time to symptom deterioration/worsening will be defined as the time from randomisation until the date of the first clinically meaningful symptom deterioration/worsening (an increase in the score from baseline of ≥ 10) that is confirmed at the next available subsequent assessment at least 14 days apart, or death (by any cause) in the absence of a clinically meaningful symptom deterioration/worsening, regardless of whether the patient withdraws from IP or receives another anti-cancer therapy prior to symptom deterioration/worsening. Missed visits are allowed in between assessments confirming deterioration/worsening. This is considered a conservative approach whereby a deterioration/worsening is considered a 'negative' outcome and therefore should be assigned as such, regardless of missed visits. Death will be included as an event only if the death occurs within 2 visits of the last PRO assessment where the symptom change could be evaluated. Patients with a single deterioration/worsening and no further assessments will be treated as deteriorated in the analysis.

Patients whose symptoms (as measured by EORTC QLQ-C30 and QLQ-LC13) have not shown a clinically meaningful deterioration/worsening and who are alive at the time of the analysis will be censored at the time of their last PRO assessment where the symptom could be evaluated. Also, if symptoms deteriorate after 2 or more missed PRO assessment visits or the patient dies after 2 or more missed PRO assessment visits, the patient will be censored at the time of the last PRO assessment where the symptom could be evaluated, prior to the 2 missed assessment visits. The 2 missed visit rule for ePRO will take a 'look-forward' approach i.e. if there are 2 consecutive missed visits at any time prior to the confirmed deterioration event, the event will be censored at the last available assessment prior to the 2 missed visits. Confirmation of deterioration will be first determined, then the censoring rules will be applied.

See Appendix A for further details on the derivation of the confirmation of deterioration 2 missed visit rule for ePRO and length of 2 missed visit window.

If the patient has no evaluable visits or does not have baseline data, they will be censored at day 1 unless they die within 2 visits of baseline (8 weeks plus 3 days allowing for a late assessment within the visit window).

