The population for the analysis of time to symptom deterioration will include patients who have baseline scores of ≤ 90 .

Time to HRQoL/function deterioration/worsening (QLQ-C30)

For HRQoL and function (as measured by EORTC QLQ-C30), time to deterioration/worsening will be defined as the time from the date of randomisation until the date of the first clinically meaningful deterioration/worsening (a decrease in the function scales or the global health status/QoL score from baseline of ≥ 10) that is confirmed at the next available subsequent assessment at least 14 days apart, or death (by any cause) in the absence of a clinically meaningful deterioration/worsening, regardless of whether the patient withdraws from IP or receives another anti-cancer therapy prior to HRQoL/function deterioration/worsening. Missed visits are allowed in between assessments confirming deterioration. This is considered a conservative approach whereby a deterioration is considered a 'negative' outcome and therefore should be assigned as such, regardless of missed visits. Death will be included as an event only if the death occurs within 2 visits of the last PRO assessment where the HRQoL/function change could be evaluated. Patients with a single deterioration/worsening and no further assessments will be treated as deteriorated in the analysis.

Patients whose HRQoL or function have not shown a clinically meaningful deterioration/worsening and who are alive at the time of the analysis will be censored at the time of their last PRO assessment where the HRQoL/function could be evaluated, prior to the 2 missed visits. Also, if HRQoL or function deteriorates after 2 or more missed PRO assessment visits or the patient dies after 2 or more missed PRO assessment visits, the patient will be censored at the time of the last PRO assessment where HRQoL/function could be evaluated. The 2 missed visit rule for ePRO will take a 'look-forward' approach i.e. if there are 2 consecutive missed visits at any time prior to the confirmed deterioration event, the event will be censored at the last available assessment prior to the 2 missed visits. Confirmation of deterioration will first be determined, then the censoring rules will be applied. If the patient has no visits or does not have baseline data, they will be censored at day 1 unless they die within 2 visits of baseline (8 weeks plus 3 days allowing for a late assessment within the visit window).

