8 APPENDIX

APPENDIX A. 2 MISSED VISITS

ePRO Assessments

As per Section 3.2.3.1, confirmation of deterioration/worsening will first be determined, then the censoring rules will be applied. For ePRO assessments, we will apply a ‘look-forward’ approach to the 2 missed visit rule.

For example:

Baseline	V1	V2	V3	V4	V5	V6	V7	V8	Observed confirmed deterioration visit*	Time to Deterioration derivation
	NC	DT	DT	NC	MV	NC	IMP	NC	Event at V2	Event at V2
	MV	MV	NC	DT	MV	DT	DT	NC	Event at V4	No event, censor at baseline
	MV	DT	NC	MV	MV	DT	DT	NC	Event at V6	No event, censor at V3
	NC	DT	NC	MV	IMP	DT	NC	DT	Event not confirmed, but if last DT then confirmed	Event at V8

	NC	DT	NC	MV	IMP	DT	MV	DT	Event at V6	Event at V6
	NC	IMP	NC	IMP	MV	MV	IMP	DT	Event at V8, last DT	No event, censor at V4
	MV	MV	NC	MV	MV	DT	DT	NC	Event at V6	No event, censor at baseline
	NC	DT	MV	MV	DT	NC	IMP	DT	Event at V2	Event at V2

DT Deterioration; IMP Improvement; MV Missed visit; NC No change (/stable).

*Missed visits are allowed in between assessments confirming deterioration/worsening, and confirmation of deterioration/worsening requires at least 14 days between assessments.

Length of 2 missed visit window for EORTC QLQ-C30 and QLQ-LC13

The scheduled visit assessments and visit windows for the QLQ-C30 and QLQ-LC13 are every 4 weeks (± 1 week) for the first 8 weeks from randomization, and then every 8 weeks (± 1 week) up to 48 weeks relative to date of randomization, and then every 12 weeks (± 1 week) until confirmed PD by RECIST 1.1 per Investigator assessment, and then every 12 weeks (± 1 week) thereafter until PFS2.

Missing baseline or within 2 visits of baseline:

- A patient without baseline will be censored at day 1 unless they die \leq day 63.
- Any assessment \leq day 63 is within 2 visits (2×4 weeks + 1 week) of baseline and therefore cannot be censored for missing visits.

Schedule: q4w ± 1 week:

For any assessment $>$ day 1 then visit schedule is q4w ± 1 week and thus the maximum time between 2 consecutive assessments is $7+28+28+7=70$ days.

Schedule: q8w ± 1 week:

- For any assessments where the visit schedule changes from q4w ± 1 week to q8w ± 1 week, the maximum time between 2 consecutive assessments is $7+28+56+7 = 98$ days.
- For any assessments where the visit schedule is q8w ± 1 week, the maximum time between two consecutive assessments is $7+56+56+7 = 126$ days.

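### The PRO missed-visit rule removes deteriorations seen after a gap but keeps event-free follow-up after the same gap, so time to deterioration is overstated

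*SAP*

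**What the plan says.** For symptom scales, SAP 3.2.3.1 treats three kinds of patient.

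- **Alive, no deterioration:** the patient "will be censored at the time of their last PRO assessment where the symptom could be evaluated". No missed-visit condition is attached.
- **Deterioration after a gap:** "if there are 2 consecutive missed visits at any time prior to the confirmed deterioration event, the event will be censored". The censoring date then goes back to the assessment that preceded the gap. The gap may come at any earlier time, even if stable assessments follow it.
- **Death after a gap:** "or the patient dies after 2 or more missed PRO assessment visits, the patient will be censored", again before the gap.

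The order of operations is explicit: "Confirmation of deterioration will be first determined, then the censoring rules will be applied".

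The HRQoL/function paragraph in the same section repeats the look-forward sentence but moves one phrase. There it is the non-deteriorating patient who "will be censored at the time of their last PRO assessment where the HRQoL/function could be evaluated, prior to the 2 missed visits". The sentence on deterioration or death after a gap no longer says that censoring is before the gap.

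Both paragraphs define death within two visits of baseline as "8 weeks plus 3 days allowing for a late assessment within the visit window". Appendix A handles the same case differently: "A patient without baseline will be censored at day 1 unless they die" by day 63.

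Time to deterioration is listed as a secondary endpoint in SAP 1.1.2 and SAP 6. SAP 4.2.3 analyses it by stratified log-rank test, with hazard ratios on a forest plot and Kaplan-Meier plots.

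**The concern.** A censoring rule is neutral only if the decision to censor at a given time does not use what happens later. Here two patients with identical data up to and through a gap are treated differently according to their later assessments. The one who deteriorates or dies loses all time after the gap, and the event with it. The one who stays stable keeps that time in the risk set. Post-gap follow-up thus adds to the denominator and never to the numerator, so the hazard after a gap is understated even when visits are missed purely at random.

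The size of the error grows with the frequency of gaps. If the arms differ in missed visits, the arm with more of them looks better without any treatment effect.

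The rule also works against an aim stated in the same section, where it is called conservative to accept a deterioration despite missed visits between the confirming assessments. SAP 4.2.1 gives PFS attrition-bias analyses that restore actual event times after missed assessments. Time to deterioration has no counterpart.

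**Working it through.** **1. Reproducing Appendix A.** The symptom rule was coded as follows. Take the first deterioration (DT) confirmed at the next available assessment, or a DT at the last assessment. If two consecutive missed visits (MV) precede it, censor at the last assessment before the first such gap. If there is no event, censor at the last assessment. All 8 of the 8 Appendix A rows reproduce.

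**2. Same gap, different later outcome.** In the four rows censored for a gap, each DT was changed to no change (NC) and the same rule applied.

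| Appendix A pattern, V1–V8 | SAP result | Result with DT changed to NC |
|---|---|---|
| MV MV NC DT MV DT DT NC | censored at baseline | censored at V8 |
| MV DT NC MV MV DT DT NC | censored at V3 | censored at V8 |
| NC IMP NC IMP MV MV IMP DT | censored at V4 | censored at V8 |
| MV MV NC MV MV DT DT NC | censored at baseline | censored at V8 |

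The gaps are identical and only the assessed outcomes differ. All eight Appendix A rows contain a deterioration, so no example shows what happens to a stable patient with a gap.

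**3. Size when single visits are missed at random.** Inputs from the documents: the PRO schedule (weeks 4, 8, 16, 24, 32, 40, 48, 60, 72, 84, 96) and the 85% compliance goal in Protocol 9.4.3.3, which means 15% missed. Assumed inputs: sustained deterioration, true median 48 weeks, independent misses, 20,000 patients per arm. Ranges are over repeated independent runs.

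| Missed visits | Observed deteriorations discarded | 48-week estimate, SAP rule (true 0.50) |
|---|---|---|
| 15% | 10–11% | 0.52 |
| 25% | 25% | 0.54–0.55 |

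The steep rise follows from the chance that two given adjacent visits are both missed: 0.15² = 0.0225 against 0.25² = 0.0625, a factor of 2.8.

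With no treatment effect, the hazard ratio (fewer-missed arm over more-missed arm) should be 1:

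| Missed, arm vs arm | SAP rule | Everyone censored before the gap |
|---|---|---|
| 15% vs 25% | 1.11–1.15 | 0.98–1.02 |
| 15% vs 30% | 1.20–1.23 | 0.98–1.02 |

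Read the other way, the arm with more missed visits would show 1/1.15 = 0.87 to 1/1.11 = 0.90 in the first case and 1/1.23 = 0.81 to 1/1.20 = 0.83 in the second.

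**4. Size when misses cluster.** A second simulation let a two-visit gap start with probability g at each visit (true median 52 weeks, data cut-off at 72 to 168 weeks, no deaths). The share of visits missed is 2g/(1+g).

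| g | Visits missed | Week-96 estimate, SAP rule | Everyone censored before the gap | True |
|---|---|---|---|---|
| 0.05 | 0.10/1.05 = 9.5% | 0.348 | 0.280 | 0.278 |
| 0.10 | 0.20/1.10 = 18.2% | 0.419 | 0.284 | 0.278 |
| 0.15 | 0.30/1.15 = 26.1% | 0.516 | 0.284 | 0.278 |

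With no treatment effect and g of 0.05 against 0.15, the hazard ratio (more gaps over fewer) is 0.71 under the SAP rule and 1.01 when everyone is censored before the gap.

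**5. Death window.** SAP 3.2.3.1: 8 × 7 + 3 = 59 days. Appendix A: 2 × 28 + 7 = 63 days. The PRO visit window in the protocol's schedule of activities and in Appendix A is ±1 week, which matches 63 and not 59.

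**The case against.** The strongest reply is about consequence. Time to deterioration is outside the multiple testing procedure, which holds only PFS and OS. Protocol 9.5.1.9 names the mixed-model change from baseline as the primary PRO analysis, and that model does not use this rule. The hazard-ratio bias needs the arms to differ in missed visits. With 15% missed in both arms and a true effect, one simulation gave 0.789 under the SAP rule against 0.795 with complete data; with no effect and 15% against 20% missed, it gave 1.07. The trial is double-blind up to the PFS analysis, and compliance is tabulated by arm and visit, so a large imbalance would be visible. All of this stands, and it limits the point to how the PRO hazard ratios and curves are read.

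The remedy is also partly a choice. Counting every observed deterioration regardless of gaps gave 48-week estimates of 0.508 and 0.523 at 15% and 25% missed, with null hazard ratios of 1.02–1.03, and it discards nothing. If sicker patients skip visits, censoring everyone before a gap is itself informative. That supports adding a second analysis; it does not support keeping the present rule.

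The HRQoL/function wording may be no more than a misplaced phrase, since it is missing from the next sentence, where the symptom paragraph has it. Even so, the literal text gives a programmer two different rules. The 59- versus 63-day mismatch is real but touches very few patients. The general promise in SAP 3.2.3.1 to handle systematic missing data names no method.

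**Conclusion.** The rule is wrong as written for symptom scales. That censoring depends on the later outcome follows from the text and from Appendix A, with no assumption needed. For HRQoL/function the literal text does not clearly carry the same asymmetry, and the two paragraphs conflict. The death window is also inconsistent.

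The size rests on assumed medians and missing-visit patterns that the documents do not give. At the protocol's compliance goal with independent misses, the distortion is modest: about 2 percentage points at week 48, with little effect on the hazard ratio when the arms miss equally. It becomes material when misses cluster, when they reach about 25%, or when the arms differ by 10 points or more. The change should be made while it remains a matter of wording. It does not affect the primary or key secondary conclusions.

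**What to change.** 1. Use one rule, in the same words, for symptoms and for HRQoL/function: any patient with two consecutive missed PRO visits before a confirmed deterioration or death is censored at the last evaluable assessment before the first such gap, whether or not an event follows.
2. Add rows to Appendix A for patients with a gap and no deterioration, including one with stable assessments after the gap.
3. Replace 8 weeks plus 3 days with day 63 in both paragraphs, so that they agree with Appendix A and the ±1 week window.
4. Add a sensitivity analysis that counts all observed deteriorations and deaths regardless of gaps, parallel to the attrition-bias analysis for PFS in SAP 4.2.1.

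The cost is SAP wording and programming; no data collection changes. The downside is that stable patients with a gap lose their post-gap follow-up in the main analysis. The sensitivity analysis keeps that follow-up and shows whether it matters.

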3.2.3.2 Compliance rate

Summary measures of overall compliance and compliance over time will be derived for each EORTC-QLQ-C30 and EORTC-QLQ-LC13, respectively. These will be based upon:

- Received questionnaire = a questionnaire that has been received and has a completion date and at least one individual item completed.
- Expected questionnaire = a questionnaire that is expected to be completed at a scheduled assessment time, i.e., a questionnaire from a patient who has not withdrawn from the study at the scheduled assessment time but excluding patients in countries with no available translation. For patients that have progressed, the latest of progression and safety follow-up will be used to assess whether the patient is still under PRO follow-up at the specified assessment time. Date of study discontinuation will be mapped to the next closest visit date to define the number of expected forms.
- Evaluable questionnaire = a questionnaire with a completion date and at least one subscale that is non-missing.

- Overall PRO compliance rate is defined as: Total number of evaluable questionnaires across all time points, divided by total number of questionnaires expected to be received across all time points multiplied by 100.
- Overall patient compliance rate is defined for each randomised treatment group as: Total number of patients with an evaluable baseline and at least one evaluable follow-up questionnaire (as defined above), divided by the total number of patients expected to have completed at least a baseline questionnaire multiplied by 100.

Compliance over time will be calculated separately for each visit, including baseline, as the number of patients with an evaluable questionnaire at the time point (as defined above), divided by number of patients still expected to complete questionnaires. Similarly, the evaluability rate over time will be calculated separately for each visit, including baseline, as the number of evaluable questionnaires (per definition above), divided by the number of received questionnaires.

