ADA Anti-drug antibody; AE Adverse event; ALK Anaplastic lymphoma kinase; C Cycle; CT Computed tomography; ECG Electrocardiogram; ECOG Eastern Cooperative Oncology Group; EGFR Epidermal growth factor receptor; EORTC QLQ-C30 European Organisation for Research and Treatment of Cancer 30-item core quality of life questionnaire; HIV Human immunodeficiency virus; ICF Informed consent form; IP Investigational Product; iv Intravenous; LFT Liver function test; miRNA Micro ribonucleic acid; MRI Magnetic resonance imaging; mRNA Messenger ribonucleic acid; NSCLC Non-small cell lung cancer; PD Progression of disease; PD-L1 Programmed death ligand 1; PK Pharmacokinetic; q4w Every 4 weeks; q8w Every 8 weeks; q12w Every 12 weeks; q28d Every 28 days; QLQ-LC13 13-item self-administered questionnaire for lung cancer; RNA Ribonucleic acid; SAE Severe Adverse Event; RECIST Response Evaluation Criteria in Solid Tumors; T3 Triiodothyronine; T4 Thyroxine; TSH Thyroid-stimulating hormone; WHO World Health Organization; WT Body weight.

AstraZeneca

	Time since last dose of IP								
	Day (±3)			12 months					
Evaluation	30	2	3	4	6	8	10	then every 2 months (±2 weeks) ^a	For details, see Section
EORTC QLQ-C30, QLQ-LC13, and EQ-5D-5L as well as health resource use (HOSPAD) ^b	Participant questionnaires and information related to health resource use should be completed relative to the date of Cycle 1 Day 1 visit date(i.e. date of randomization/first dose) as follows: $q4w$ (± 1 week) for the first 8 weeks, every 8 weeks ± 1 week thereafter for the first 48 weeks (per Table 1), then every 12 weeks ± 1 week thereafter until PFS2.								
Physical examination (full)	Х								8.2.2
Vital signs (temperature, respiratory rate, blood pressure, and pulse)	Х								8.2.3
Weight	Х	X	X						8.2.3
Pregnancy test ^c	X As clinically indicated						8.2.1		
AE/SAE assessment	Х	X	X						8.3
Concomitant medications	Х	X	X						6.4
WHO/ECOG performance status	At timepoints consistent with tumour assessments; at 30, 60, and 90 days after treatment discontinuation; and then at initiation of subsequent anticancer therapy ^d							8.2.5	
Subsequent anticancer therapy ^e and second progression assessment ^{f, g}	<>					8.1			
Survival status ^h		X	X	Х	X	X	Х	X	8.1.2
Haematology	Х	X	X						Table 8
Clinical chemistry	Х	X	X						Table 7
TSH (reflex free T3 or free T4 ⁱ)	Х	X	X						Table 7
PK assessment			Х						8.5

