During the Treatment Period, participants who are clinically stable at an initial Response Evaluation Criteria in Solid Tumors 1.1-defined radiological progression of disease may continue to receive study treatment at the discretion of the Investigator and participants. A follow-up scan is to be collected after the initial Response Evaluation Criteria in Solid Tumors 1.1-defined radiological progression of disease, no less than 4 weeks after the prior assessment of progression of disease and no later than the next regularly scheduled imaging visit, and this scan is evaluated using the Confirmation of Radiological Progression criteria outlined in Appendix E. Participants with confirmed PD who continue to receive study treatment at the discretion of the Investigator and participant (following consultation with AstraZeneca) can receive treatment until no longer having clinical benefit, and tumor
assessments should continue on their regular imaging schedule for the duration of treatment. If the subsequent scan does not confirm the immediate prior radiological progressive disease, scanning should continue until the next Response Evaluation Criteria in Solid Tumors 1.1defined radiological progression of disease, which in turn will require a subsequent scan evaluated using the Confirmation of Radiological Progression criteria outlined in Appendix E.

Follow-up of participants post discontinuation of study treatment

Participants who have discontinued study treatment due to toxicity or symptomatic deterioration, clinical progression, or who have commenced subsequent anticancer therapy will be followed up with tumour assessments until Response Evaluation Criteria in Solid Tumors 1.1-defined radiological progression of disease plus an additional follow-up scan or until death (whichever comes first) and followed for survival. PRO questionnaires will be followed up until PFS2.

Survival

All participants randomised in the study should be followed up for survival.

Independent Data Monitoring Committee:

The Independent Data Monitoring Committee will meet periodically in accordance with the IDMC charter to review safety assessments and make recommendations to continue, amend, or stop the study based on safety findings.

Full details of the Independent Data Monitoring Committee procedures and processes can be found in the Independent Data Monitoring Committee Charter.

Statistical methods

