3.2.2.6 Time to death or distant metastasis (TTDM)

TTDM (per RECIST 1.1 as assessed by BICR) will be defined as the time from the date of randomisation until the first date of distant metastasis or death in the absence of distant metastasis. Distant metastasis is defined as any new lesion that is outside of the radiation field according to RECIST 1.1. For this reason, the TTDM endpoint will be determined from recurrent disease that occurs outside of the structures contained within the thorax, including lymph nodes, pulmonary, pleural, and mediastinal metastatic sites and excluding the heart. The locations of distant metastases will be defined and documented prior to database lock/unblinding.

Patients who have not developed distant metastasis or died at the time of analysis will be censored at the time of the latest date of assessment from their last evaluable RECIST 1.1 assessment. However, if the patient has distant metastasis or dies after 2 or more missed visits, the patient will be censored at the time of the latest RECIST 1.1 assessment prior to the 2 missed visits. If the patient has no evaluable visits or does not have baseline data, they will be

censored at Day 1 unless they die within 2 visits of baseline, which then will be treated as an event with date of death as the event date.

3.2.2.7 **Time from randomisation to second progression or death (PFS2)**

Time from randomisation to second progression or death (PFS2) will be defined as the time from the date of randomisation to the earliest of the progression event subsequent to first subsequent therapy, or death.

There are two preconditions to have PFS2 second progression event: 1) observation of primary PFS event (first progression) by Investigator; 2) received subsequent anti-cancer therapy. The primary PFS event includes only radiological progression by RECIST 1.1, as per Investigator.

The date of second progression will be recorded by the Investigator in the eCRF and defined according to local standard clinical practice and may involve any of the following: objective radiological imaging, symptomatic progression, or death. Second progression status will be reviewed ($q8w \pm 1$ week for the first 48 weeks [relative to the date of randomisation] and then $q12w \pm 1$ week [the first progression]) following the first progression event used for the primary variable PFS and status recorded.

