3.2.3 Patient-reported outcomes (PRO)

Symptoms and overall quality of life (QoL) will be assessed using the PRO questionnaires, European Organisation for Research and Treatment of Cancer (EORTC) 30-item core (QoL) questionnaire (QLQ-C30) ([Aaronson et al 1993](#)) and 13-item lung cancer QoL questionnaire (QLQ-LC13) ([Bergman et al 1994](#)) (secondary endpoints). All questionnaires will be scored according to published guidelines or the developer's guidelines, if published guidelines are not available. All PRO data will be collected until PFS2.

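### The SAP's compliance rule stops expecting PRO forms from progressed patients before PFS2, where collection ends, and so overstates form compliance; SAP section 6 does not list the change

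*SAP*

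**What the plan says.** **When collection ends.** Protocol Table 2, which covers patients off treatment, continues the questionnaires every 12 weeks "week thereafter until PFS2". The synopsis agrees: "PRO questionnaires will be followed up until PFS2". So does SAP 3.2.3: "All PRO data will be collected until PFS2". SAP Appendix A gives the 12-weekly schedule as running "until confirmed PD by RECIST 1.1 per Investigator assessment, and then every 12 weeks" until PFS2. Protocol Table 1 ends the on-treatment schedule at confirmed progression by site review, but Table 2 takes over from there.

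**What counts as expected.** Protocol 9.4.3.3 counts a form as expected at a scheduled time if the participant has not withdrawn from the study; it excludes only countries without a translation. It also sets a compliance target of 85%, to be monitored during the trial. SAP 3.2.3.2 repeats that definition and then adds a rule for progressed patients: "the latest of progression and safety follow-up will be used to assess whether the patient is still under PRO follow-up".

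**How the rates are formed.** The overall PRO rate is "Total number of evaluable questionnaires across all time points, divided by total number of questionnaires expected to be received across all time points". The by-visit rate is the number of patients with an evaluable form "divided by number of patients still expected to complete questionnaires". SAP 4.2.6.1 uses the same derivations for EQ-5D compliance.

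**What SAP section 6 lists.** It gives two departures from the protocol: the added time-to-deterioration endpoint, and the removal of biopsy from the TTDM definition. The compliance cut-off is not among them.

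**The concern.** A compliance rate should set the forms received against the forms the schedule asked for. Here the schedule asks for forms until PFS2, while the denominator closes at the later of progression and safety follow-up. A form missed between those dates appears nowhere. A form returned there can still be counted, because the overall numerator takes every evaluable form.

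The completeness of forms after progression matters for reading the PRO results. Time to deterioration (SAP 3.2.3.1) counts deterioration regardless of stopping treatment or starting new therapy. The MMRM (SAP 4.2.3) deliberately includes discontinuation and follow-up visits within 12 months. SAP 3.2.3.1 also makes the handling of missing data depend on whether the missingness looks systematic, and this rate cannot show late missingness. Arms that progress at different times would be distorted by different amounts, and the protocol's 85% target would be read against a denominator that does not match the schedule.

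**Working it through.** The plan states no figure to reproduce. The mismatch follows from the text; only its size needs assumptions.

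**One patient (assumed timeline).** PRO visits fall at weeks 0, 4, 8, 16, 24, 32, 40 and 48, then every 12 weeks. Take progression and last dose at week 24, PFS2 at week 60, and a 90-day safety follow-up.

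- SAP cut-off: 24 + 90/7 = week 36.9. Expected forms are those at weeks 0, 4, 8, 16, 24 and 32, so 6.
- Schedule to PFS2: add weeks 40, 48 and 60, so 9.
- Forms returned only up to the cut-off: 6/6 = 100% by the SAP rule, 6/9 = 67% on the schedule.
- All forms returned, numerator as written: 9/6 = 150%.

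**General form.** Let f be the share of forms due to PFS2 that fall after the cut-off, r1 the return before the cut-off and r2 the return after it.

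- Rate on the real schedule: r1(1 − f) + r2·f = r1 − (r1 − r2)f.
- SAP rate with only expected forms in the numerator: r1. It overstates when f > 0 and r2 < r1.
- SAP rate with the numerator as written: [r1 − (r1 − r2)f]/(1 − f). It overstates whenever f > 0.

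**Assumed inputs.** r1 = 85%; r2 = 60%; last dose at progression; 90-day safety follow-up; 36 months' follow-up; exponential times; every first PFS event a progression in a survivor; no form expected after PFS2. The median PFS values, 5.6 and 16.8 months, are the placebo and durvalumab medians of the earlier trial in protocol 2.3.1. The median gap from progression to PFS2 is not in the documents, so a range is shown. The shares f come from 400,000 simulated patients per case; the other columns follow from the formulas.

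| Median PFS (months) | Median gap to PFS2 (months) | f | Rate to PFS2 | SAP rate, matched numerator | SAP rate, numerator as written |
|---|---|---|---|---|---|
| 5.6 | 1.5 | 3.8% | 84.0% | 85% | 87% |
| 5.6 | 3 | 12.4% | 81.9% | 85% | 94% |
| 5.6 | 6 | 25.8% | 78.6% | 85% | 106% |
| 5.6 | 12 | 39.2% | 75.2% | 85% | 124% |
| 16.8 | 1.5 | 1.6% | 84.6% | 85% | 86% |
| 16.8 | 3 | 5.5% | 83.6% | 85% | 88% |
| 16.8 | 6 | 12.4% | 81.9% | 85% | 94% |
| 16.8 | 12 | 20.3% | 79.9% | 85% | 100% |

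Example (5.6 months, 6-month gap): 0.85 − 0.25 × 0.258 = 0.786; as written, 0.786/(1 − 0.258) = 1.06.

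With a matched numerator the overstatement runs from 85 − 84.6 = 0.4 points to 85 − 75.2 = 9.8 points. With last dose 8 weeks after progression, the largest value falls to about 8 points.

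**The case against.** **What stands.** The table is descriptive. No PRO endpoint is in the multiple testing procedure (protocol 9.1). The overall patient compliance rate and the evaluability rate do not use this cut-off. MMRM data stop at 12 months, and time to deterioration has its own two-missed-visit censoring. SAP 4.2.3 tabulates expected, received and evaluated counts, so a rate above 100% would be noticed, though missed late forms would not. Treatment may continue past progression, which moves safety follow-up later and shrinks the effect. The protocol leaves PRO detail to the SAP, so leaving this out of section 6 is a lapse in documentation and no more.

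**What does not rescue the rule.** Protocol Table 1 stops PROs at confirmed progression, but it covers the treatment period and Table 2 carries them on to PFS2.

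**Stronger readings that the documents do not support.** A reader might infer that the rule also keeps forms expected after a non-fatal PFS2 that precedes the cut-off, so that compliance could be understated. But SAP 3.2.3.2 ties an expected form to a scheduled assessment time, and none is scheduled after PFS2. The error runs one way.

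A reader might also say that the cut-off is undefined because SAP 3.3.3 puts safety follow-up at 30 days. That is a rule for reporting ECG data. Protocol 6.4, 8.3.2 and 8.4.1, and the death summaries in SAP 4.2.5.1, use 90 days. Stating the days in SAP 3.2.3.2 would be a tidy-up.

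**Conclusion.** The concern holds as a minor point. The rule in SAP 3.2.3.2 contradicts the collection schedule in both documents and narrows the protocol's expected-form definition without being listed in section 6. Followed as written, it hides forms missed between the cut-off and PFS2 in the overall, by-visit and EQ-5D compliance rates.

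Confidence in the mismatch is high because it is on the page. The size is conditional: about 0.4 to 10 points with a matched numerator, and more, possibly above 100%, with the numerator as written. It rests on the assumed fall in return from 85% to 60% and on the assumed gap to PFS2. If return does not fall after the cut-off, the matched rate is not overstated. Deaths as the first PFS event would shrink the effect. No efficacy conclusion changes.

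**What to change.** In SAP 3.2.3.2, replace the sentence on progressed patients with: *For patients who have progressed, questionnaires are expected at every scheduled assessment until the earliest of PFS2, death, study withdrawal or DCO; only expected questionnaires count in the numerator.* List the departure from protocol 9.4.3.3 in SAP section 6.

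Alternatively, keep the shorter window but apply it to numerator and denominator alike, state it in days, label the rate as compliance to that cut-off, and report compliance from the cut-off to PFS2 separately. List this in section 6 as well.

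The cost is SAP wording, a re-derived numerator and denominator, and one line in section 6. No new data are needed.

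A separate small correction belongs in the same edit. SAP 3.2.3.1 twice gives the two-visit limit for deaths after baseline as 8 weeks and 3 days (8 × 7 + 3 = 59 days), while Appendix A uses day 63 (9 × 7). Change both places to 8 weeks plus 1 week (day 63), to match the ±1 week PRO window and Appendix A.
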